5.2 PARTICIPANT EXCLUSION CRITERIA

Any individual meeting any of the following exclusion criteria at baseline will be excluded from the study:

- 1. Must not be pregnant, breastfeeding, or trying to become pregnant. Pregnancy status will be confirmed using urine pregnancy test at the enrollment visit and again at the first visit of the second and third conditions. Participants will be instructed to use a barrier method of birth control during the study.
 - Justification: Administration of ovarian hormones to a pregnant woman could negatively influence the pregnancy in a variety of ways, including risks to the health of the fetus.
- 2. Must not be taking any form of **exogenous hormones** or IUD, and must have ended previous use of hormonal preparations at least one month prior to the study. Potential participants who were previously taking oral contraceptives or other hormonal medications must have one normal menstrual cycle (menstrual period) prior to enrollment in the study.
 - **Justification**: The use of additional exogenous hormones poses safety risks and would undermine experimental control of hormones.
 - Participants will be required to use licensed barrier methods of contraception during study participation; if they are unable to commit to this responsibility, they will not be eligible for participation.
- **3.** Must report no personal history of any **chronic medical condition**, including but not limited to metabolic or autoimmune disease, epilepsy, endometriosis, cancer, diabetes, cardiovascular, gastrointestinal, hepatic, renal, or pulmonary disease, and no personal or multiple first degree family history of thromboembolic events.
 - Justification: Administration of exogenous hormones to females with these chronic medical conditions may increase the risk of an adverse health-related response to hormones. Further, the purpose of the present study is to determine the impact of hormonal stabilization (vs. natural withdrawal) in otherwise physically *healthy* females.
- 4. Must not currently smoke cigarettes.
 - **Justification**: Administration of ovarian hormones to females who smoke may increase the risk of thromboembolic events.
- 5. Must not report a history of clinical diagnosis of postpartum depression or premenstrual dysphoric disorder (Note: PMDD diagnosis must have been made based on prospective daily ratings).
 - Justification: Some evidence would suggest that the pattern of perimenstrual symptoms that have been linked with these reproductive mood disorders *could* differ meaningfully³⁹ from that which we be expect in the more general clinical population of females with suicidality⁸. Because these distinctions are not yet clear, females with a self-reported history of clinical diagnosis with these disorders will be excluded.
- **6.** Must not report any history of manic episode, psychotic symptoms, or substance use disorder.

- Justification: These factors are known sources of variability in suicidality and would therefore introduce error into our models as well as increasing the risk that a participant would experience a suicidal crisis during the study^{1,149}.
- **7.** Must not test positive for opioid use, cocaine use, or methamphetamine use at the enrollment visit.
 - Justification: Use of these drugs are indicative of either a chronic medical condition or increased risk of suicidal crisis, both of which are exclusionary in the present study.¹⁴⁹

5.3 STRATEGIES FOR RECRUITMENT AND RETENTION

Recruitment and Informed Consent

We will utilize the same strategies for recruitment as were used in the similar preceding experiment: (1) social media advertisements with links to a qualtrics eligibility survey, and (2) community flyers with contact information.

Potential participants will complete initial eligibility screening by telephone and a secure online questionnaire.

No more information will be asked of participants than necessary to obtain eligibility information and to contact those who appear to be eligible to schedule a screening/enrollment visit. At this initial visit, the PI ([name]) will obtain written informed consent for further screening regarding suicidality from those individuals who pass the initial telephone and questionnaire screenings and are interested in participating. This consent will inform participants regarding the nature of the questions to be asked. If the participant consents, the Self-Injurious Thoughts and Behaviors Interview¹⁶⁰ and the Scale for Suicidal Ideation Interviews¹⁶⁸ will be administered. If the participant is not eligible for the study following the screening (see details above), they will be dismissed and referred for treatment as necessary. If they are eligible, [name] will obtain additional written informed consent for participation in the larger study (i.e., the screening visit will become the enrollment visit). During the consenting process for the larger study, all of the applicable consent forms will be reviewed with each individual, and they will be given as much time as they would like to discuss their participation with their significant others and decide whether to participate.

INCLUSION OF WOMEN AND MINORITIES

Men will not be included in this study, given the stated purpose of examining ovarian hormone withdrawal as a mechanism of suicidal risk in females. With respect to ethnic and racial diversity, The University of Illinois at Chicago (UIC) Women's Mental Health Research Program (WMHRP) has a strong commitment to the enrollment of racial minority women in research projects, and this commitment will be reflected in the proposed work. The WMHRP has extensive experience with recruitment and retention of diverse samples in women's mental health studies that reflect Chicago demographics. We plan to recruit proportions of ethnic and racial minorities for the proposed work that are as consistent with the demographics of Chicago (per 2016 data) as possible. We have conservatively estimated our ability to recruit a sample (N=30) that is 60% Caucasian (n = 18), 32% Black or African American (n=9), 5% Asian (n = 2), and with 3% identifying as more than one race (n = 1). With regard to ethnicity, we estimate that 25% (n = 7) will identify as Hispanic, and 75% (n = 23) will identify as non-Hispanic.

JUSTIFICATION FOR INCLUSION OF INDIVIDUALS WITH CURRENT SUICIDALITY

As reviewed in the study background and rationale, the purpose of the study is to examine the impact of natural perimenstrual hormone withdrawal (vs. prevention of hormone withdrawal/stabilization of E2 or P4) on within-person changes in suicide risk. The present sampling strategy **ensures generalizability**³ of our findings to clinical populations of interest (i.e., not simply depressed females, but those with suicidality) and will also prevent a floor effect (i.e., zero-inflation of daily outcome measures and associated limitations in power to detect effects) on primary daily outcome measures (e.g., mediating behavioral constructs, suicidality).

Individuals with current suicidality **are not necessarily at imminent risk for suicidal crises/attempt** (i.e., their risk is manageable on an outpatient basis through frequent clinical contact, such as the daily calls in the present study). Because the hormone protocol simply prolongs the physiologic luteal hormone profile, it is not expected to expose participants to additional risk of suicidal crisis beyond what they would naturally experience during their typical monthly menstrual cycles. However, out of an abundance of caution, we will **exclude females with elevated imminent risk for suicidal crisis/attempt** (determined by structured interview and established guidelines). Individuals with histories of suicidality often have ongoing, habitual thoughts about death or suicide that are highly distinguishable from **imminent risk for suicide attempt**. In further support of this notion and of the feasibility of recruiting this population, it should be mentioned that up to 1/3 of the American population experiences suicidal ideation at some point in their lives, yet less than .01% die by suicide each year.

RETENTION OF INDIVIDUALS WITH SUICIDALITY

Although a variety of exclusion criteria will be applied, the PIs recent work has prepared her to recruit, retain, and maintain the safety of participants and potential participants with suicidal ideation but low imminent risk of attempt. Furthermore, the majority of individuals with suicidal ideation do not evidence imminent risk for suicide attempt, supporting the feasibility of recruiting from this population. With regard to retention, the PI has demonstrated the capacity to recruit and retain females with BPD with suicidal ideation, and participants with BPD in her recent study have completed 85% of daily email surveys; given larger incentives for shorter daily contacts, we expect a higher response rate. In the recently-completed experimental study, the PI and her team were successful in retaining 30 participants with suicidality through a similar 4-month study.

Empirically-supported strategies for retention will include study branding, frequent contact, monetary rewards, and graduated compensation schedules.

Study subjects will receive the following monetary incentives:

Participants who complete the protocol in full will receive \$2650, paid in installments over 6-7 months of participation following the completion of the enrollment visit and folling each of three conditions.

Study participants will receive the following monetary incentives:

CLEAR 2 Study Protocol: Hormones and Suicide Risk, Version 9, 07-02-2020, Page 25 of 64

- \$150 pay for one enrollment visit
- \$150 pay for each laboratory testing session x 9 laboratory sessions (= \$1350 total)
- \$250 for completing daily online symptom surveys in each condition (=total \$750)
- \$100 for completing daily phone calls in each condition (=total \$300)
- \$100 for debriefing visit

Rationale for Pay: The compensation structure utilized here is identical to that used for the previous iteration of this experiment (the K99-funded experiment) at the PI's previous institution (UNC Chapel Hill). It is critical that the compensation structure remain identical in order to prevent any possible change to the protocol that may affect participant investment or attitudes toward completion of surveys and laboratory visits. The extended nature of the protocol (6-7 months) and the intensive requirements of participation coincide with the level of incentive we are providing. Given the intensive nature of the study and the long time-span over which compensation will be provided, we believe that this compensation structure is NOT likely to be coercive.

5.4 PARTICIPANT WITHDRAWAL OR TERMINATION

5.4.1 REASONS FOR WITHDRAWAL OR TERMINATION

Participants are free to withdraw from participation in the study at any time upon request. An investigator may terminate participation in the study if:

- Any clinical adverse event (AE), or other medical condition or situation occurs such that continued participation in the study would not be in the best interest of the participant (severe mood deterioration, severe changes in suicidality, severe hormonal side effects), as determined by [name] in collaboration with [name] (or the DSMB).
- The participant meets an exclusion criterion (either newly developed or not previously recognized) that precludes further study participation.

5.4.2 HANDLING OF PARTICIPANT WITHDRAWALS OR TERMINATION

PROTOCOL FOR DISCONTINUATION AND REFERRAL

If a participant shows emergence of severe mood symptoms or greater than low risk of suicide attempt, the URWAP protocol for assessing and managing suicide risk will be closely followed (see Appendix for UWRAP). In particular, if a participant appears to need immediate treatment, our offices are in close proximity to UIC emergency department, and participants requiring immediate emergency care can easily be escorted there. The blind will be broken for the participant and their study participation will be discontinued. If it is revealed that the participant was currently in the placebo condition, they will simply be referred to their mental health provider (or, as necessary, to the emergency department) for treatment. However, if it is supervising physician ([name]) will oversee a gradual tapering of the hormonal intervention and the patient will be referred to their mental health provider (or, as necessary, the emergency will oversee a gradual tapering of the hormonal intervention and the patient will be referred to their mental health provider (or, as necessary, the emergency will oversee a gradual tapering of the hormonal intervention and the patient will be referred to their mental health provider (or, as necessary, the emergency department) for treatment.

5.5 PREMATURE TERMINATION OR SUSPENSION OF STUDY

Administration of study agent will be halted when three serious AEs* determined to be "probably related" (i.e., with new onset during study patches/pills) are observed. The PI will immediately notify the DSMB when this occurs. The DSMB will notify the study sponsor and investigators immediately when the third severe event is reported and enrollment screens will stop accepting new study participants. The DSMB will request the statistical analyses and tables that they wish to review, and these will be prepared by an unblinded biostatistician associated with the study. All requested documentation will be provided to the DSMB. The DSMB will convene an ad hoc meeting by teleconference or in writing as soon as possible. The DSMB will provide recommendations for proceeding with or terminating the study to the PI and the NIH. The study sponsor will inform all appropriate regulatory agencies of the temporary halt and the disposition of the study (i.e., terminate, continue).

*Statistically, the most likely examples of serious adverse events in the present study include development of a venous thromboembolism or a suicide attempt during an experimental phase of the study.

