4 STUDY DESIGN AND ENDPOINTS

4.1 DESCRIPTION OF THE STUDY DESIGN

This is a single-center study; there is no phase designation because it is a mechanistic experiment with agents (E2,P4) that is commonly used in clinical practice.

Participants: 60 female outpatients (recruited to achieve a targed N of 40 completers) with a with past-month suicidal ideation but **low**^{17,18} **imminent suicide risk** (see **Human Subjects**) receiving treatment as usual. Participants must: be 18 to 45 years of age, have normal menstrual cycles (21-35 days), not pregnant, breastfeeding, or trying to get pregnant, not taking hormones, no history of serious medical illness, normal weight (BMI 18-29.99), and low risk for thrombotic events (factor V Leiden mutation based on family history). *Most outpatients with suicidality take medications; therefore, to increase feasibility/generalizability, medication use will be measured and covaried in analyses (as in the similar study recently completed by the PI).*

Psychiatric Diagnoses. The SCID-I and SCID-II. *History of manic episode, psychosis, or substance abuse disorder will be exclusionary due to risk of suicidal crises*^{17,100}. Additionally, self-report history of postpartum depression or premenstrual dysphoric disorder are exclusionary, since reproductive mood disorders may be characterized by a different pattern of sensitivity¹⁰¹. Based on data from the preceding study, we expect 90% of our sample to have lifetime depressive disorder, 50% to meet criteria for BPD, and 50% to have lifetime anxiety disorder.

Study Design (Fig 2). THIS IS NOT A CLINICAL EFFICACY

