8.2.2 RELATIONSHIP TO STUDY AGENT

For all AEs, [name] will urgently collaborate with [name] to determine the AE's causality based on temporal relationship and clinical judgment. The degree of certainty about causality will be graded using the categories below.

Definitely Related – There is clear evidence to suggest a causal relationship, and other possible contributing factors can be ruled out. The clinical event occurs in a plausible time relationship to drug administration and cannot be explained by concurrent disease or other drugs or chemicals. The response to withdrawal of the drug (dechallenge) should be clinically plausible. The event must be pharmacologically or phenomenologically definitive, with use of a satisfactory rechallenge procedure if necessary.

Probably Related – There is evidence to suggest a causal relationship, and the influence of other factors is unlikely. The clinical event occurs within a reasonable time after administration of the drug, is unlikely to be attributed to concurrent disease or other drugs or chemicals, and

CLEAR 2 Study Protocol: Hormones and Suicide Risk, Version 9, 07-02-2020, Page 38 of 64

follows a clinically reasonable response on withdrawal (dechallenge). Rechallenge information is not required to fulfill this definition.

Possibly Related – There is some evidence to suggest a causal relationship (e.g., the event occurred within a reasonable time after administration of the trial medication). However, other factors may have contributed to the event (e.g., the participant's clinical condition, other concomitant events). Although an AE may rate only as "possibly related" soon after discovery, it can be flagged as requiring more information and later be upgraded to "probably related" or "definitely related," as appropriate.

Unlikely to be related – A clinical event whose temporal relationship to drug administration makes a causal relationship improbable (e.g., theevent did not occur within a reasonable time after administration of the trial medication) and inwhich other drugs or chemicals or underlying disease provides plausible explanations (e.g., theparticipant's clinical condition, other concomitant treatments).

Not Related – The AE is completely independent of study drug administration, and/or evidenceexists that the event is definitely related to another etiology. There must be an alternative, definitive etiology documented by [name] or [name].

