10.4 DESCRIPTION OF STATISTICAL METHODS

10.4.1 GENERAL APPROACH

The design of this study is a three-period crossover design, where each of three study periods is a perimenstrual frame of the menstrual cycle (days +7 to +22 following ovulation where positive ovulation test day=0). Each participant will complete all three conditions in a randomized order.

Primary hypothesis tests will be evaluated using a alpha level of .05, with a two-tailed test.

All outcomes will be checked for normality; given the low likelihood that suicidality will follow a normal distribution even in this clinical sample, we expect that we will need to utilize nonparametric procedures.

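### The only numeric halting rule leaves out serious adverse events that begin after patches and pills end on day +21, even when graded probably or definitely related

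*Combined protocol and SAP*

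**What the plan says.** Sections 5.5, 8.5 and 10.4.7.1 carry the same rule. Administration of study agent is halted at three serious AEs determined to be *probably related*, and the rule explains that term, after an *i.e.*, as "with new onset during study patches/pills". A footnote says the likeliest serious events "include development of a venous thromboembolism or a suicide attempt during an experimental phase of the study". The halt is a pause: the DSMB reviews the data and recommends whether to continue. No other count or threshold triggers a halt.

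Section 8.2.2 has its own definition of *probably related*. There must be evidence of causality, "the influence of other factors is unlikely", and a plausible response when the drug is withdrawn. On timing it says: "The clinical event occurs within a reasonable time after administration of the drug". The next grade down, *possibly related*, applies where "other factors may have contributed to the event", and the participant's clinical condition is given as an example.

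Under 7.3.3 the patch is removed and pills end on day +21 of each condition. Under 4.1 telephone measures continue for 5 days after the last patch or pill. Under 8.3 SAEs are recorded until 30 days after the last day of participation.

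**The concern.** The rule takes a term that the protocol defines elsewhere and gives it another meaning, tied to time on agent. The study is built around hormone withdrawal, so the days after the agent stops are not a neutral period:

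- Section 2.1 reports that in the preceding study perimenstrual risk moved to the withdrawal week of the active condition, about two weeks later.
- Section 2.3.1 allows that the taper ending the stabilization conditions could bring negative mood changes.
- Section 7.3.4 justifies the debriefing visit partly by risk emerging after exogenous hormones are withdrawn.

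A suicide attempt or venous thromboembolism, the two events the rule itself names, could begin shortly after removal and be graded probably related, yet add nothing to the count. Other participants would go on receiving agent unless the DSMB chose to intervene. A fixed count exists so that a pause does not depend on that choice.

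**Working it through.** The threshold of three has no stated derivation, event rate or operating characteristic, so there is no figure to reproduce. The check compares texts and counts days.

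**1. Which serious events count.** The parenthetical can be read as the definition of *probably related* (the literal sense of *i.e.*) or as a condition added to the 8.2.2 grade.

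| Serious event | Parenthetical as definition | Parenthetical plus grade | 8.2.2 grade alone | Proposed rule |
|---|---|---|---|---|
| On agent, possibly related | counts | no | no | counts |
| On agent, probably or definitely related | counts | counts | counts | counts |
| After removal, possibly related | no | no | no | DSMB decides |
| After removal, probably or definitely related | **no** | **no** | counts | counts |

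The last row is the defect. Both readings of the current text exclude an event that meets the protocol's own causality standard.

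**2. Does the footnote rescue it?** The footnote refers to an experimental phase, and 10.4.1 says "each of three study periods is a perimenstrual frame of the menstrual cycle (days +7 to +22 following ovulation". If that is the intended window, it adds one day, +22.

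**3. Days involved, per condition.**

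- On agent: days +7 to +21 = 15 calendar days (the 14-day course of 6.1.9, counting both the day of application and the day of removal).
- Post-removal call days: +22 to +26 = 5.
- First patch to last call: 15 + 5 = 20 days. Share after removal: 5/20 = 25%. Using 14 agent days instead gives 5/19 = 26%.
- If day +22 counts, 4 of the 5 remain outside: 4/20 = 20%.
- Condition C taper window in 4.1, about +16 to +22: 7 days, of which 1 falls after removal, 1/7 = 14%. The other 6 are on agent and already covered.

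These are shares of days. The documents give no SAE rate, and 2.1 says the preceding study recorded none, so they cannot be turned into shares of risk.

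**4. Would the 8.2.2 grade alone be better?** No. Section 4.1 states "we expect 90% of our sample to have lifetime depressive disorder, 50% to meet criteria for BPD". An on-agent attempt in such a participant could be graded only possibly related because of her clinical condition. It would then stop counting, although the literal rule counts it now (first row of the table).

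**5. Placebo.** Section 4.1 gives placebo the same patch and pill schedule, so 14 of 3 × 14 = 42 agent days (33%) are placebo days. Serious events on those days count under the literal rule.

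**The case against.** The best case on the other side has four parts.

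*Few events are lost.* The 8.2.2 grade requires that other explanations be unlikely and that the event respond plausibly to stopping the drug. Many post-removal suicide attempts in this population would fail that test, so removing the time limit would add few events. This stands and limits the size of the point. It does not cure it, because an event that does earn the grade is still excluded.

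*It is loose drafting.* The words *determined to be* suggest clinician grading, and the footnote speaks of an experimental phase. That is plausible, but neither reading of the parenthetical reaches past removal, and the footnote adds at most one day.

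*Other safeguards remain.* SAEs are captured (8.3). Severe AEs go to the IRB and DSMB within a week (8.4.1), as do unanticipated problems (8.4.3). Deaths and immediately life-threatening events go to the sponsor within 24 hours (8.4.2). The DSMB meets every six months and as events emerge, and can identify procedures to be altered or stopped (sections 8 and 9). Individuals can be discontinued (5.4). All of this stands. What is lost is an automatic pause, not oversight.

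*The withdrawal-risk statements are qualified.* Section 2.3.1 expects mood changes no worse than those of natural withdrawal. Section 7.3.4 refers to the placebo-then-experimental order, which looks carried over from a two-condition design. That is fair. They show the protocol acknowledges risk in this period, not that it expects excess risk.

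A reader might infer more than the documents support: that post-removal events go unmonitored, that most withdrawal-related events escape the rule, or that counting on-agent events whatever their cause is itself an error to remove. The first is contradicted by the safeguards above. The second conflicts with the Condition C taper lying mostly on agent, and no event rate exists to support it. The third would make the rule less protective (step 4 of the check).

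**Conclusion.** Wrong as written, of minor to moderate severity. Followed literally, the only automatic trigger ignores serious events that begin after day +21, whatever their causality grade, and so conflicts with 8.2.2. The effect is confined to whether a pause is automatic or left to the DSMB after prompt reporting. Its frequency cannot be estimated.

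The conclusion rests on the nominal schedule, with agent ending on day +21; visit windows of ±2 days could shift this slightly. It also assumes that *definitely related* is meant to count wherever *probably related* does. It does not depend on which reading of the parenthetical is adopted.

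**What to change.** In 5.5, 8.5 and 10.4.7.1, replace the parenthetical so that the count of three includes:

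- (a) serious AEs (8.1.2) that begin during study patches/pills, as now; and
- (b) serious AEs that begin after patches and pills end in any condition and are graded probably or definitely related under 8.2.2, with no cut-off at day +21 and up to the 30-day recording limit in 8.3.

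Leave to the DSMB whether post-removal events graded possibly related should also count. In the same three places change the third *severe* event to the third *serious* event: severity (8.2.1) and seriousness (8.1.2) are separate scales.

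The cost is amendment wording. No new data are needed, because causality is already graded for all AEs and SAEs are already recorded past removal. The downside is a slightly higher chance of a temporary halt, including from events in placebo cycles. If the sponsor currently intends the grade to be required on agent as well, (a) would also add on-agent serious events graded below probably related. That intention should be settled in the same amendment.
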